7 APPENDIX

7.1 Laboratory Data Conversion and Transformation Rules

- Conversion to Système International (SI) Units
Laboratory data should be stored on the database in the units in which they were originally delivered by the laboratory.
For analysis and reporting purposes, the data will be converted to SI units to allow the comparison of data delivered in different original units.
Results that include inequality sign will be converted into a numeric form removing inequality sign.
Results that cannot be converted into an expected numeric form nor interpreted, such as alphabetic entries like “adequate”, will usually not be further processed, but displayed in patient listings.
- Marked Laboratory Abnormalities
For each laboratory test, a Marked Abnormality Range has been defined. A value outside of this range is considered to be potentially clinically relevant. This Marked Abnormality Range is wider than the Reference Range.
In addition, for each laboratory test, a percentage change, as an increase and/or decrease, has been defined which represents a clinically relevant change from baseline.
A Marked Abnormality is therefore defined as a test result:
which is outside of the Marked Abnormality Range,
and
which also represents a clinically relevant change from baseline of at least the designated amount
during or within 30 days after end of trial treatment.
Baseline is taken as the last valid value before starting treatment. If no baseline is available, the midpoint of the Reference Range will be substituted for processing purposes for determination of Marked Abnormalities.
For urinalysis a missing baseline value will be replaced by 0 (zero).
NOTE: For calculating means and mean changes over time, missing values will not be included. If no baseline is available, no change from baseline will be calculated.
Values above and below the Reference Range are flagged on the listing by H and L, respectively. Marked Abnormalities are flagged by HH or LL.

● Reference Ranges

Laboratory Test Class	Laboratory Test	SI Unit	Reference Range [1,2]	Marked Abnormality Range	Direction of Change	Clinically Relevant Change from Baseline
Hematology	Hematocrit	fraction	M: 0.37 – 0.49 F : 0.36 – 0.46 ^b	0.31 – 0.56	Increase Decrease	≥ 15% ≥ 15%
	Hemoglobin	g/L	M: 130 – 180 F : 120 – 160 ^b	110 – 200	Increase Decrease	≥ 15% ≥ 15%
	Leukocytes (WBC)	10 ⁹ /L	4.5 – 11.0	3.0 – 18.0	Increase Decrease	≥ 30% ≥ 30%
	Platelets	10 ⁹ /L	150 – 350	100 – 550	Increase Decrease	≥ 50% ≥ 30%
	Mean corpuscular hemoglobin (MCH)	pg/cell	25.0 – 35.0	21.2 – 40.2	Increase Decrease	≥ 15% ≥ 15%
	Mean corpuscular hemoglobin concentration (MCHC)	g/L	310 – 370	260 – 430	Increase Decrease	≥ 15% ≥ 15%
	Mean corpuscular volume (MCV)	fL	78 – 100	66 – 115	Increase Decrease	≥ 15% ≥ 15%
	Erythrocytes (RBC)	10 ¹² /L	M: 4.50 – 5.30 F : 4.10 – 5.10 ^b	3.80 – 6.10	Increase Decrease	≥ 15% ≥ 15%
Differentials	Bands	10 ⁹ /L	0 – 0.70	0 – 1.40	Increase	≥ 30%
	Bands	fraction	0 – 0.05	0 - 0.10	Increase	≥ 30%
	Basophils	10 ⁹ /L	0 – 0.20	0 – 0.40	Increase	≥ 100%
	Basophils	fraction	0 – 0.03	0 – 0.06	Increase	≥ 100%
	Lymphocytes	10 ⁹ /L	1.00 – 4.80	0.70 – 7.60	Increase Decrease	≥ 30% ≥ 30%
	Lymphocytes	fraction	0.16 – 0.46	0.10 – 0.72	Increase Decrease	≥ 30% ≥ 30%
	Monocytes	10 ⁹ /L	0 – 0.80	0 – 1.70	Increase	≥ 100%
	Monocytes	fraction	0 – 0.11	0 – 0.22	Increase	≥ 100%
	Neutrophils	10 ⁹ /L	1.80 – 7.70	1.50 – 9.25	Increase Decrease	≥ 20% ≥ 20%
	Neutrophils	fraction	0.45 – 0.75	0.37 – 0.90	Increase Decrease	≥ 20% ≥ 20%
	Eosinophils	10 ⁹ /L	0 – 0.45	0 – 0.90	Increase	≥ 100%
Coagulation	Prothrombin Time, normalized ratio (PTINR)	ratio	0.70 – 1.30	≤ 2.00	Increase	≥ 30%
	Partial Thromboplastin Time, activated (PTT)	seconds	22.1 – 34.1	0 – 45	Increase	≥ 40%
	Fibrinogen	g/L	1.75 – 4.00 ^a	≥ 1.30	Decrease	≥ 30%
	Antithrombin 3	fraction	0.80 - 1.30	≥ 0.60	Decrease	≥ 20%
Heart Function	ASAT (SGOT)	U/L	M: 0 – 40 ^c F : 0 – 25 ^b	0 – 80	Increase	≥ 50%
	Lactic Dehydrogenase (LDH)	U/L	0 – 210 ^c	0 – 420	Increase	≥ 50%
	Creatine phosphokinase (CPK) total	U/L	M: 60 – 400 ^a F : 40 – 150 ^b	≤ 800	Increase	≥ 50%
	CPK (MB Fraction)	µg/L	0 – 5 ^c	≤ 5	Increase	0%

Laboratory Test Class	Laboratory Test	SI Unit	Reference Range [1,2]	Marked Abnormality Range	Direction of Change	Clinically Relevant Change from Baseline
Liver Function	Alkaline Phosphatase	U/L	M: 0 – 115 ^c F : 0 – 100 ^b	0 – 220	Increase	≥ 50%
	ALAT (SGPT)	U/L	M: 0 – 55 ^c F : 0 – 30 ^b	0 – 110	Increase	≥ 50%
	Total Bilirubin	μmol/L	0 – 17 ^c	0 – 34	Increase	≥ 75%
	Direct bilirubin	μmol/L	0 – 7 ^c	0 – 14	Increase	≥ 75%
	γ-GTP	U/L	M: 0 – 94 ^c F : 0 – 70 ^b	0 – 190	Increase	≥ 50%
Renal Function	BUN	mmol/L	2.9 – 8.9	0 – 14.3	Increase	≥ 50%
	Creatinine	μmol/L	0 – 133	0 – 154	Increase	≥ 50%
Thyroid Function	Triiodothyronine (T3)	nmol/L	0.92 – 2.78	0.74 - 3.30	Increase Decrease	≥ 20% ≥ 20%
	Thyroxine (T4)	nmol/L	58 – 140	30 - 164	Increase Decrease	≥ 20% ≥ 20%
	Free T4	pmol/L	10 – 36	5 – 40	Increase Decrease	≥ 20% ≥ 20%
	TSH	mU/L	0 – 5.0 ^c	0 – 10.0	Increase	≥ 30%
Protein	Albumin	g/L	35.0 – 55.0	≥ 30	Decrease	≥ 20%
	Total Protein	g/L	60 – 80	55 – 87	Increase Decrease	≥ 20% ≥ 20%
Lipid Chemistry	Triglycerides (fasting)	mmol/L	0.45 – 1.69	0 – 2.83	Increase	≥ 100%
	Cholesterol	mmol/L	0 – 6.18	0 – 8.30	Increase	≥ 30%
	LDL-Cholesterol	mmol/L	0 – 4.13	0 – 5.4	Increase	≥ 30%
	HDL-Cholesterol	mmol/L	≥ 0.91	≥ 0.65	Decrease	≥ 30%
Electrolytes	Chloride	mmol/L	100 – 108	95 – 115	Increase Decrease	≥ 7% ≥ 7%
	Potassium	mmol/L	3.4 – 4.8	2.9 – 5.8	Increase Decrease	≥ 20% ≥ 20%
	Sodium	mmol/L	135 – 145	130 – 150	Increase Decrease	≥ 7% ≥ 7%
	Bicarbonate	mmol/L	22 – 26	18 – 28	Increase Decrease	≥ 20% ≥ 20%
	Calcium	mmol/L	2.10 – 2.60	2.00 – 2.90	Increase Decrease	≥ 10% ≥ 10%
	Phosphorus inorganic	mmol/L	0.84 – 1.45	0.75 – 1.60	Increase Decrease	≥ 30% ≥ 30%
	Blood Glucose (fasting)	mmol/L	3.90 – 6.10	2.80 – 11.10	Increase Decrease	≥ 75% ≥ 75%
	Uric Acid	μmol/L	M: 214 – 506 F: 137 – 393 ^b	0 – 600	Increase	≥ 50%
Urinalysis Dipstick	Proteinuria	1 to 6	1 – 3	1 – 3	Increase	≥ 2 units ^d
	Glycosuria	1 to 6	1 – 3	1 – 3	Increase	≥ 2 units ^d
	Hematuria	1 to 6	1 – 3	1 – 3	Increase	≥ 2 units ^d
	Leukocyturia	1 to 6	1 – 3	1 – 3	Increase	≥ 2 units ^d
Urinalysis Microscopic ^e	Casts	/HPF	0 – 2	0 – 2	Increase	≥ 2 units
	WBCs	/HPF	0 – 2	0 – 2	Increase	≥ 2 units
	RBCs	/HPF	0 – 2	0 – 2	Increase	≥ 2 units
	Urinary spec. gravity ^f	No unit	1.001 – 1.035	not defined	not defined	not defined

- a) For reporting and analyzing, the data are linearly transformed to the Reference Range according to the formula below.
- b) For reporting and analyzing, the data for females are linearly transformed to the Reference Range

- for males according to the formula below.
- c) For reporting and analyzing, the data are linearly transformed to the Reference Range according to the formula below.
To prevent transformed values becoming negative, the investigator lower limit is replaced by zero.
 - d) Note that baseline values of 5 and 6 do not allow a subsequent clinically relevant change.
 - e) To be done if dipstick is positive and microscopic examination needed for specific quantitation/confirmation.
 - f) Specific gravity is a measurement of solute load in the urine. It is increased markedly by both proteinuria and glycosuria.
A value > 1.030 in the absence of proteinuria or glycosuria is most commonly caused by radiographic contrast. In volume depletion specific gravity is usually >1.020. A fixed value of 1.010 (isosthenuria) is characteristic of chronic renal impairment. A fixed value of 1.000 - 1.005 occurs in diabetes insipidus. Specific gravity has an important influence on urine microscopy because cells lyse more rapidly in dilute urine, which may lead to considerable inaccuracies in quantitation of cells. Cells swell and rupture in dilute urine and shrink in concentrate urine. Casts are rarely seen at low urine osmolality [5].
Conclusion: increase or decrease in urine specific gravity clinically relevant in context with other parameters from urinalysis.

Note: The following modification is applied to creatinine and TSH as needed.

Creatinine: The transformation of data described above as c) is applied for only Japanese patients study as needed.

TSH: The lower limit of the reference range and Marked Abnormal Range are modified and Clinically Relevant Change from Baseline for decrease is provided as needed.

- **Formula for Linear Transformation**

$$R_T = S_L + [(R_U - I_L) / (I_H - I_L)] * (S_H - S_L)$$

R_T : transformed value

R_U : untransformed value

I_L : I_H investigator limits, low and high

S_L : S_H reference limits, low and high

For female to male transformation replace I_L , I_H by the reference limits for female, and S_L , S_H by the reference limits for male.

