#### **4.5.2.2 Assessments during Treatment**

Assessment during treatment applies to both double-blind and extension period. All assessments must be performed on the day of the specified visit, unless a time window is specified in the schedule of assessments (see [Appendix 1](#)). Assessments scheduled on the day of study drug administration should be performed prior to administration of study drug, unless otherwise noted in the schedule of assessments.

If study drug cannot be administered on the scheduled visit, every effort should be made to perform the assessments at the visit.

If a patient misses a scheduled visit without notice, the Investigator and/or site staff should try to contact the patient via telephone or another way in order to confirm if there has been an AE or relapse.

The Investigator and/or site staff should encourage the patient to visit the study site for an assessment as soon as possible.

*Following the implementation of Protocol Version 11, administration of satralizumab prefilled syringes outside of the study site may be allowed, in accordance with local*

*regulations, only if no on-site assessments are scheduled for that dosing day (Appendix 1). Patients should be followed up by phone to monitor if there has been an AE or neurological worsening.*

*During extraordinary circumstances like the SARS-CoV-2 (COVID-19) pandemic, when patients cannot attend a study site for a scheduled visit, administration of satralizumab outside of the study site will be allowed for all scheduled dosing days during the OLE period after Week 48 (Appendix 1). Patients should be followed up by phone around the time of the scheduled visit to confirm patient compliance with study drug treatment, and to collect information on safety and/or neurological worsening the patient might experience. Safety laboratory assessments may be performed at a local laboratory when possible and any clinically significant abnormal laboratory values reported as AEs in the eCRF as described in Section 5.3.5.*

Please see [Appendix 1](#) for the schedule of assessments performed during the treatment period.

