#### **4.5.2.3 Assessments at Last Observation Visit/Withdrawal Visit**

The Withdrawal (WD) Visit is for patients who withdraw from the study. Every effort should be made to conduct the visit at 12 weeks ( $\pm 7$  days) after the last dosing. Patients aged 12 to 17 years at the time of informed consent who withdraw from the study will attend the WD visit at 12 weeks ( $\pm 7$  days) after last dosing for follow-up assessments for adolescents (see Section 4.5.2.5). At the WD Visit of double-blind period, a complete set of the assessments performed every 24 weeks after Week 48 of double-blind period are to be performed (plus a chest X-ray). At the WD Visit of extension period, a complete set of the assessments performed every 24 weeks from Week 0 to Week 48 of extension period are to be performed (including a chest X-ray) with the exception of the anti-AQP4Ab assay.

Patients who experience a relapse which is treated with rescue therapy and/or a protocol-defined relapse which is adjudicated by CEC or who complete the double-blind period can enter the OLE period. Patients completing the OLE period will attend a Last Observation Visit 12 weeks after the last dose of satralizumab.

The Last Observation Visit will be conducted 12 weeks after the last dose of satralizumab for patients who complete the OLE period. At this visit, a complete set of the assessments performed at Week 0 of extension period are to be performed (including a chest X-ray) with the exception of the anti-AQP4Ab assay. *Patients who complete the OLE period with the last study drug administration on or before 31 December 2021 and decide to continue treatment with satralizumab outside of this study will not have to complete the Last Observation Visit.*

After the Last Observation Visit or WD Visit, AEs should be followed as outlined in Sections 5.5 and 5.6.

Please see [Appendix 1](#) for the schedule of assessments performed at the Withdrawal Visit and the Last Observation.

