#### **5.3.1 Adverse Event Reporting Period**

Investigators will seek information on AEs at each patient contact. All AEs, whether reported by the patient or noted by study personnel, will be recorded in the patient's medical record and on the Adverse Event pages of the eCRF.

After informed consent has been obtained but prior to initiation of study drug, only SAEs caused by a protocol-mandated intervention should be reported (e.g., SAEs related to invasive procedures of the protocol). These SAEs will be recorded in the Drug Safety database and not on the Adverse Event eCRF.

After initiation of study drug, all AEs, regardless of relationship to study drug, will be reported on the eCRF until the Withdrawal Visit or Last Observation (12 weeks after the last dose of study drug). After this period, investigators should report any deaths, SAEs, or other AEs of concern that are believed to be related to prior treatment with study drug (see Section 5.6).

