## **6.6 SAFETY ANALYSES**

All safety analyses will be performed on the SAF. Safety variables to be assessed are AEs, AESIs, SAEs, selected AEs, injection site reactions, patient withdrawals due to AEs, change in 12-lead ECGs, measurements of laboratory parameters, and vital signs (including body weight).

Summary tables for number and percentage of patients with adverse drug reactions (i.e., AEs related to study drug) will be tabulated.

Adverse events will be summarized by System Organ Class and preferred term, based on Medical Dictionary for Regulatory Activities coding, and grade of severity. The incidence of treatment emergent AEs will also be displayed by severity and relationship to the study drug, respectively. In addition, the incidence of AEs leading to withdrawal from treatment and SAEs will be tabulated.

Incidence of Selected AEs (see Section 5.2.4) will be tabulated. IRRs will be further analyzed according to whether they meet Sampson's criteria for diagnosis of anaphylaxis (Sampson et al, 2006).

Laboratory values (including hematology, blood chemistry, and urinalysis), frequencies of laboratory abnormalities, vital signs (temperature, SBP, DBP and pulse rate), physical examination, 12-lead ECG, and suicidality (C-SSRS) will be summarized. Measurement and change from Baseline in continuous laboratory parameters (hematology, clinical chemistry, and urinalysis), continuous ECG, vital signs (blood pressures and pulse rate), and body weight will be summarized using descriptive statistics. When analyzing categorical data, the number and percentage of patients in each category will be presented. In addition, shift tables may be used to evaluate the number and percentage of patients having a different post-baseline status when compared to their baseline status. Numbers of patients who meet the marked abnormality criteria will also be presented.

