**Appendix 1: Schedule of Activities (cont.)**

**Table 6: Observation and Test Schedule in the Screening Period and the Double-Blind Period (cont.)**

Week	Double-blind period				WD g)	SFU h)	FUAA i)
	After Week 48		Extra visit at relapsing	DOW q)			
	Every 4 weeks	Every 24 weeks					
Window in days	±7	±7	-	-	-	-	±7
Immunogenicity							
Anti-drug antibody	X	X			X		X j)
CCSR c, p)							
Serum		X	X		X		
Plasma		X	X		X		

- a) RBC, Hb, HCT, WBC, WBC differentiation, PLT, INR, fibrinogen, total protein, albumin, total bilirubin, ALP, AST, ALT,  $\gamma$ -GTP, LDH, total cholesterol, LDL, HDL, triglyceride, ferritin, BUN, creatinine, CK, Na, Cl, K, Ca, P, complement (CH50, C3, C4), uric acid, urinary glucose, urinary protein, urinary occult blood, urobilinogen.
- b) IL-6, sIL-6R, hsCRP.
- c) The sampling is optional and will require a separate signature on the informed consent.
- d) Blood sample for plasmablasts will be collected in United Kingdom, France, Germany, Japan and Taiwan.
- e) For females of child-bearing potential. Serum or urine  $\beta$ -hCG [sensitivity of at least 25 mIU/mL] will be performed. For patients aged 12 to 17 at the time of informed consent, urine  $\beta$ -hCG will be recommended (see [Appendix 13](#)).
- f) Safety Follow-Up will be conducted for patients who withdraw from the study in double-blind period due to clinical relapse and will last for 24 weeks from the last dosing. A telephone interview will be conducted by site personnel every 4 weeks from last dosing to identify any new or worsening neurological symptoms.
- g) For patients who withdraw from the study. Every effort should be made to conduct the visit at 12 weeks after the last dosing. Patients aged 12 to 17 years at the time of informed consent who withdraw from the study will attend WD visit at 12 weeks ( $\pm 7$  days) after last dosing for FUAA.
- h) Window in days is within  $\pm 28$  days.
- i) Visual function testing is not required if it is implemented with FSS assessment.
- j) ECG should be performed prior to blood draws.
- k) Information on concomitant medication/therapy for NMO and NMOSD will be collected.
- l) ZBI is optional and will be performed for caregiver who signed informed consent to caregiver burden assessment.

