5.11.9 Clinical Laboratory Evaluation

For continuous laboratory measurements including hematology, clinical chemistry, and urinalysis, summary using descriptive statistics of the actual values and their change from baseline will be presented by treatment group at each visit. The laboratory tests to be performed are presented in Table 4-4.

When analyzing categorical data, the number and percentage of subjects in each category will be presented. In addition, shift tables may be used to evaluate the number and percentage of subjects having a different post-baseline status when compared to their baseline status.

A subject data listing will be provided for all laboratory data. Values outside the normal range will be flagged within the listing. A subject data listing will also be provided for all treatment emergent marked laboratory abnormalities (see Section 7.1).

The following summaries, listings and figures will be provided:

- A summary of each laboratory parameter in Table 4-4 and change from baseline will be provided by visit.
- A shift table based on the normal range for each laboratory parameter will be presented by double-blind period endpoint value relative to baseline by treatment group.
- A by-subject listing of laboratory parameters.

The summaries above will be provided by treatment group.

Table 4-4 Laboratory measurements

Hematology	Clinical chemistry	Urinalysis	Complement
Hematocrit	Calcium	Glucose	Complement tests (C3, C4 and CH50)
Hemoglobin	Phosphorus	Protein	
International normalized ratio	Serum electrolytes (sodium, potassium, chloride)	Urinary occult blood	
Platelet count	Ferritin	Urobilinogen	
Red blood cell (RBC) count	Albumin		
WBC count	Total serum protein		
Absolute differential count (neutrophils, eosinophils, lymphocytes, monocytes, basophils, other cells)	Blood urea nitrogen (BUN)		
	Creatinine		
	Uric acid		
	Alkaline phosphatase		
	AST		
	ALT		
	GGT		
	Total bilirubin		
	Fibrinogen		

	Lactate dehydrogenase (LDH) Total cholesterol Low density lipoprotein (LDL) cholesterol High density lipoprotein (HDL) cholesterol Triglycerides Creatine kinase (CK)		
--	--	--	--

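### If end of trial treatment means the last dose, the 30-day limit for marked laboratory abnormalities in SAP 7.1 leaves out the on-time 12-week Withdrawal Visit sample

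*SAP*

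**What the plan says.** SAP 7.1 calls a result a marked abnormality if it lies outside a set range, differs from baseline by a set amount, and occurs "during or within 30 days after end of trial treatment". Such values are flagged HH or LL. They feed two outputs. SAP 5.11.9 states: "A subject data listing will also be provided for all treatment emergent marked laboratory abnormalities". Protocol 6.6 adds a count: "Numbers of patients who meet the marked abnormality criteria will also be presented".

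Protocol 4.5.2.3 sets the final laboratory samples. For patients who withdraw: "Every effort should be made to conduct the visit at 12 weeks" (plus or minus 7 days) after the last dosing. For the extension: "The Last Observation Visit will be conducted 12 weeks after the last dose of satralizumab for patients who complete the OLE period". The Appendix 1 tables mark a laboratory test at both visits. On dosing days, Protocol 4.5.2.2 says: "Assessments scheduled on the day of study drug administration should be performed prior to administration of study drug".

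The adverse event period is longer. Protocol 5.3.1 says: "After initiation of study drug, all AEs, regardless of relationship to study drug, will be reported on the eCRF until the Withdrawal Visit" or the Last Observation, 12 weeks after the last dose. SAP 1 treats all adverse events collected in the study as treatment-emergent. The safety periods in SAP 5.2 run to the clinical cutoff date, the end of study or last contact. The double-blind period also stops on the day before the first extension dose. Neither period has a 30-day cut.

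**The concern.** The 30-day allowance and the 12-week visit do not meet. A marked fall in neutrophils or platelets, or a marked rise in liver enzymes or lipids, found at an on-time Withdrawal Visit would not be flagged or counted as a marked abnormality. An adverse event starting on the same day would be in the adverse event tables. The two outputs would cover different risk periods, and nothing in the SAP says that this is intended.

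The same section lists tests that this trial does not measure, such as T3, T4 and TSH. This suggests standard text that was not fitted to the trial's visit schedule.

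**Working it through.** There is no stated figure to reproduce. The check compares visit days with the limit.

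**Inputs**
- Limit: 30 days after the end of treatment (SAP 7.1).
- Final visit: 12 weeks plus or minus 7 days after the last dose (Protocol 4.5.2.3; for Last Observation, the 12 weeks are there and the window is in Table 7).
- Dosing interval: 4 weeks, 28 days.

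**1. Treatment ends at the last dose (SAP 5.11.1)**
- 12 × 7 = 84; 84 − 7 = 77 and 84 + 7 = 91.
- Excess over the limit: 77 − 30 = 47 days to 91 − 30 = 61 days.
- 0 of the 15 allowed days qualify.

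**2. Treatment ends one dosing interval after the last dose**
- 77 − 28 = 49 and 91 − 28 = 63.
- Excess: 49 − 30 = 19 days to 63 − 30 = 33 days. Still 0 of 15.

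**3. Treatment ends at the end of study (the SAP 5.2 period for All SA237)**
- The final sample counts. But the 30-day allowance then has almost nothing to act on, because no safety laboratory test is scheduled after that visit. Safety Follow-Up is by telephone (Protocol 4.5.2.4), and the later adolescent visits record adverse events and anti-drug antibodies.

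**4. A sample about 4 weeks after the last dose** (a patient off drug whose 4-weekly double-blind visits continue, or extension Week 0)
- 28 − 7 = 21 to 28 + 7 = 35.
- Days 21 to 30 qualify, so 10 of 15 allowed days are inside the limit.

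**Consequence for one patient.** Take a patient who receives a dose, leaves, and next attends at 12 weeks. The dosing-day sample is pre-dose and cannot show that dose's effect. The next scheduled sample is outside the limit. After extension Week 48, Table 7 has laboratory tests every 12 weeks, not every 4. The last countable scheduled sample can then precede up to three doses: the one on that day and those 4 and 8 weeks later.

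**The case against.** Four objections have weight.

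- **The term is undefined.** On the end-of-study reading the final sample counts. This is correct, but that reading empties the 30-day clause (step 3), so the last dose is the more natural meaning. The ambiguity needs repair in any case.
- **The extension is largely outside this SAP.** It was written for Protocol Version 8.0, and its safety periods stop at the clinical cutoff, the onset day of the 26th event (SAP 7.4). Extension completers come later. This stands: the Last Observation part applies only if the rule is reused.
- **A 30-day flag can be a deliberate choice.** SAP 5.2 drops PK samples taken more than 6 weeks after the last administration, citing IgG half-life, so a value at days 77 to 91 may be mostly washout. This stands as a reason to show such values separately. It does not explain a limit shorter than the SAP's own safety period.
- **The values are not lost.** They stay in the laboratory listing with range flags. The AST/ALT table uses the maximum post-baseline value with no 30-day limit. Clinically significant results are reported as adverse events (Protocol 5.3.5.4). This also stands.

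A reader might infer that no sample after treatment can ever count. The documents do not support this. Patients taken off drug may remain in the study (Protocol 4.7.1.1), the extra visit at relapse has a laboratory test, and a Withdrawal Visit held early can fall within 30 days.

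A reader might also infer that patients who stop for a laboratory problem are hit hardest. Nothing shows this, because the value that prompts stopping would normally be seen on treatment and would count.

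Nor can a percentage of missed samples be stated. It would need an assumed distribution of visit days, and 4-weekly laboratory visits that do not continue after extension Week 48.

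**Conclusion.** The point holds in a limited form. With the last dose as the end of treatment, the SAP 7.1 limit excludes every on-time Withdrawal Visit sample (0 of 15 allowed days, 47 to 61 days late). That sample is inside the 12-week adverse event period. It is also inside the SAP 5.2 safety period, provided that it precedes the clinical cutoff and that end of study there means the patient's own last visit. Some patients who leave the study may have no scheduled sample reflecting their last dose in the marked-abnormality outputs.

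The effect is confined to the HH/LL flag, one listing and one descriptive count. It does not touch the efficacy analyses. The number of patients affected cannot be derived from the documents. The change is still worth making, because it is cheap and concerns a pre-specified safety output.

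**What to change.** In SAP 7.1:

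1. Define end of trial treatment as the date of the last dose.
2. Replace the 30-day limit with the SAP 5.2 periods: the double-blind period for safety analysis, and for All SA237 the SA237 exposure duration, including its clinical cutoff limit.
3. Flag values more than 30 days after the last dose, so that washout values can be read separately.
4. Say where the extension Week 0 sample belongs. It is taken before the first extension dose, but on the day after the double-blind period ends.

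The cost is a sentence or two in the SAP and one programming condition. Because SAP 5.11 already ties the safety analyses to these periods, counts can only stay the same or rise. The downside is that they will include some washout values, which the flag makes visible.

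No change of window helps extension completers who continue satralizumab outside the study, since Protocol 4.5.2.3 releases them from the Last Observation Visit.
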